### Protocol

Up to 100 patients with chronic hepatitis B will be enrolled including at least 40 patients who have not been previously treated (naïve patients: primary study) and up to 40 patients who have received or are receiving nucleoside analogue therapy and up to 20 patients who have relapsed following withdrawal of therapy (experienced patients: salvage study). After medical evaluation and liver biopsy, patients will be randomized and receive either monotherapy with tenofovir (300 mg) daily or combination therapy with tenofovir (300 mg) and emtricitabine (FTC: 200 mg) daily. Gilead Sciences will provide the combination of tenofovir and emtricitabine as a single tablet and tenofovir 300 mg as a single tablet. Neither the investigators nor the patients will be blinded to the investigational agents. Patients will be followed carefully on therapy at 2 to 12 week intervals and undergo repeat medical evaluation and liver biopsy at 48 and 192 weeks. Therapy will be continued indefinitely, although the randomized phase of this trial will last for 192 weeks only. The definition of a successful endpoint of therapy will be the maintained suppression of HBV DNA below  $10^2$  IU/ml by current PCR-based assays, Roche Amplicor assay). Secondary endpoints will be (2) normalization of ALT levels and (3) histological improvements which are expected to occur in all patients with full suppression of HBV DNA and in a proportion of those with partial suppression. Other endpoints will be (3) loss of HBeAg and (4) loss of HBsAg. Patients who have lost HBsAg will undergo a monitored withdrawal of therapy with reinstatement of treatment if relapse occurs.

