### **E. Monitoring**

Patients will be seen, interviewed, and have blood and urine tests taken at regular intervals according to the following schedule (Appendix A): on at least two occasions during the six months before treatment (Screen 1 and 2) including at the time of liver biopsy and initial evaluation, on day 0 (before first administration of drug) and at weeks 2, 4, 8, 12, 24, 36, and 48 after starting therapy. Thereafter, the patients will be seen every 12 weeks while on therapy. At each visit, the patients will be asked about symptoms and possible side effects and fill out a symptom and side effect questionnaire. Blood samples will be drawn for CBC and biochemical tests including chemistry-20 panel (ALT, AST, alkaline phosphatase, creatine kinase, lactic dehydrogenase, direct and total bilirubin, sodium, potassium, chloride, bicarbonate, glucose, BUN, creatinine, albumin, total protein, calcium, and phosphate), and 10 ml of research blood. HBV DNA will be measured at every clinical visit during therapy and more often if needed, such as to investigate viral breakthrough. In addition, HBsAg, HBeAg and anti-HBe will be tested every 12 weeks during therapy and anti-HBs if appropriate. An additional sample will be collected for routine storage to allow for repeat testing. Urine will be collected for urinalysis and random total protein/creatinine ratio at every visit. Twenty-four hour urine for creatinine clearance and total protein will be done at 48 weeks and 192 weeks. Women of child bearing potential will have a pregnancy test at each study visit. Women with a positive pregnancy test will be immediately withdrawn from study drug/s. Patients may be offered alternative approved therapy if clinically indicated. Immunological testing for CD4+ and CD8+ T cell responses to HBV antigens will be done before treatment for all previously untreated patients and repeated at 2, 4, 8, 12, 36 and 48 weeks for HLA-A2 positive patients. Alpha-fetoprotein levels will be measured every 24 weeks. Ultrasound or computerized tomography of the liver will be done every 24 weeks months in patients with advanced fibrosis or cirrhosis; in other patients these tests will be done at the time of 48 and 192 week liver biopsies. Fibroscan of the liver will be performed yearly. Bone mineral density will be re-assessed at 48 and 192 weeks.

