## I. Statistical analysis

Superiority of combination therapy compared to monotherapy with tenofovir will be tested. The primary analysis will be conducted at 1 and 4 years on the entire study cohort (Groups A-D). A separate analysis will be conducted on previously treated subjects with resistance combining all HBeAg-positive and -negative cases. We predict the rate of full virological response to combination therapy will be 94% and to tenofovir monotherapy to be 70% at 4 years. A Fisher's exact test with a .05 two-sided significance level will have 86% power to detect the difference between a combination therapy proportion of  $\pi_1$  of .94 and a monotherapy proportion of  $\pi_2$  .70 if the sample size in each group is 50. Secondary analyses will be done within the HBeAg positive and negative stratum and the nucleos(t)ide naïve and nucleos(t)ide treated stratum. Variables to be analyzed in association with a virological response will include: baseline ALT and HBV DNA level, liver histology, HBV genotype and previous resistance. Patients with missing data or who drop out of the study will be considered as treatment failures on an intention to treat basis. For comparison of means, Student's t-test will be used. All reported p-values will be 2-sided.

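### Scoring all missing data as failure conflicts with the last-observation definition of maintained response and, if loss differs by arm, lets retention enter the primary comparison

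*Combined protocol and SAP*

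**What the plan says.** Section I (Statistical analysis) sets out the primary test: "Superiority of combination therapy compared to monotherapy with tenofovir will be tested", by a two-sided Fisher's exact test at weeks 48 and 192. Its only rule for missing data is "Patients with missing data or who drop out of the study will be considered as treatment failures on an intention to treat basis". It does not separate a missed visit from withdrawal or loss to follow-up, and gives no visit window, dropout assumption or missing-data sensitivity analysis.

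Section F (Assessment of response) names maintained full virological response at weeks 48 and 192 as the primary endpoint. It defines maintained as present at the last observation in a patient still on therapy. Under Stopping therapy, it counts discontinuation for toxicity as failure.

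Section E (Monitoring) states that "HBV DNA will be measured at every clinical visit during therapy", and visits after week 48 are 12-weekly. A missed week-48 or week-192 value will therefore usually have neighbours.

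The documents disagree on blinding. The opening of the Protocol section states "Neither the investigators nor the patients will be blinded to the investigational agents". Section D describes double-blind randomization, Section L describes weekly review without knowledge of treatment, and the Appendix A table has a medication row naming placebo.

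**The concern.** There are two separate problems.

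**Classification.** Two analysts could score the same patient differently on the primary endpoint. One following Section I fails a patient who missed week 192 but was suppressed 12 weeks before and after. One following Section F counts that patient as a responder.

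**Interpretation.** When loss is scored as virological failure, a difference in loss between arms shows up as a difference in response. Near-equal suppression is not a remote scenario. For treatment-naïve patients, question 1 under Hypotheses and Issues expects similar HBV DNA patterns in the two arms, and question 3 expects non-responders to be mostly non-compliant patients. Follow-up lasts 192 weeks. Both primary time points are also admission visits with liver biopsy (salvage patients have no biopsy at week 48), so they are demanding visits to attend. A significant result could be read as better viral suppression when part of it is better retention, and a real benefit could be hidden in the same way.

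**Working it through.** **Inputs from Section I.** "We predict the rate of full virological response to combination therapy will be 94% and to tenofovir monotherapy to be 70% at 4 years"; 50 per arm; Fisher's exact test, two-sided 0.05; stated power 86%. The section also ties the primary analysis to Groups A–D, which Section D caps at 4 × 20 = 80, or 40 per arm, so both sizes are shown.

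**Assumptions not in the documents.** Dropout rates per arm, and dropout independent of suppression.

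**Step 1: the plan's own figure.** Enumerating all 51 × 51 pairs of binomial counts and summing the probability of pairs with Fisher p ≤ 0.05, at 0.94 against 0.70 and n = 50, gives 85.7%. The stated 86% is reproduced.

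**Step 2: counted response under the rule.** With true suppression s and dropout d, counted response = s × (1 − d). With s equal in both arms, the apparent difference = s × (d_mono − d_comb). At s = 0.94, a 10-point gap in loss gives 0.94 × 0.10 = 9.4 points. Loss of 0% against 25.5% would give 0.94 against 0.94 × 0.745 = 0.70, the whole planned effect.

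**Step 3: chance of declaring combination superior when s = 0.94 in both arms** (same enumeration, this direction only; nominal ceiling 2.5%):

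| Loss, combination / monotherapy | Counted response | n = 50 per arm | n = 40 per arm |
|---|---|---|---|
| 0 / 0% | 0.940 / 0.940 | 0.5% | 0.3% |
| 10 / 10% | 0.846 / 0.846 | 1.2% | 1.3% |
| 5 / 10% | 0.893 / 0.846 | 5.4% | 4.9% |
| 5 / 15% | 0.893 / 0.799 | 17.0% | 14.2% |
| 5 / 20% | 0.893 / 0.752 | 35.9% | 29.2% |

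**Step 4: the other direction.** Loss of 20/5% gives a 35.9% chance of declaring monotherapy superior at n = 50. If the true effect is 94% against 70%, loss of 15/5% gives counted rates 0.94 × 0.85 = 0.799 and 0.70 × 0.95 = 0.665, and power falls from 85.7% to 25.8%.

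**Step 5: in patients.** Suppose 47 of 50 are truly suppressed in each arm. Eight suppressed monotherapy patients missing against none gives 47/50 against 39/50, p = 0.041. Counting one of those eight as suppressed gives 47/50 against 40/50, p = 0.071. A tipping-point table would show at once that such a result is fragile.

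**Step 6: the missed visit, passages side by side.** Consider a patient below 10^2 IU/ml at weeks 180 and 204, on the allocated drug, with no week-192 sample. Under Section I the value is missing, so the patient is a failure. Under Section F the last observation on therapy is suppressed, so the patient is a responder. Neither section says which governs.

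**The case against.** **Dropout as failure is a legitimate composite.** This stands. It also fits Section F, which already counts toxicity stops as failures. A reader might infer that the rule itself is an error; the documents do not support that. The defects are the conflict with Section F and the absence of anything to show what the rule contributes to the result.

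**The illustration rests on invented dropout.** This also stands. No document gives a dropout rate or supports a particular split between arms. Both regimens are a single tablet on the same visit schedule. If those who leave are mainly non-responders, the rule creates little false difference, and Section F does offer patients with persistent viraemia after a year the option to stop or change therapy.

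**The trial may not be open-label.** A reader might infer from the opening of the Protocol section that unblinded patients will leave at different rates. Sections D and L and Appendix A say or imply otherwise, so the documents do not settle it. The arithmetic does not need it.

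**Planned analyses might reveal the problem.** A reader might infer that nothing planned could. In fact, Hypotheses and Issues plans HBV DNA decline and slope by arm (question 1) and response at weeks 96, 144 and 240 and at last assessment (question 3). These could give some warning. They are not missing-data analyses, however, and the failure rule may carry over to the response rates.

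**A value after week 192 may not exist,** because the randomized phase ends there. Therapy continues indefinitely and week 240 is a planned assessment, so many patients should have one. Where there is none, the value simply stays a failure.

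**Conclusion.** The point holds as a fault worth correcting before analysis. The conflict between Sections F and I is certain from the text and affects classification on the primary endpoint.

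The effect of unequal loss is conditional. With equal 94% suppression, false superiority of combination is about 5%, 17% and 36% at 50 per arm for gaps of 5, 10 and 15 points starting from 5% loss, and 5%, 14% and 29% at 40 per arm. These figures assume the dropout rates and assume dropout unrelated to suppression. They show sensitivity and are not a forecast.

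A reader might infer that any difference in dropout produces a false positive. It does not. Any difference shifts the estimate, but a 5-point gap gives about 5% against a nominal 2.5%. With 47 of 50 suppressed in each arm, about eight or nine more suppressed patients must be missing from one arm than from the other. Equal loss creates no false superiority (1.2% at 10/10%). The bias has no fixed direction and can equally hide a benefit of combination.

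**What to change.** In Section I:

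1. Reconcile the missing-data rule with Section F's definition of maintained response. Count a missing week-48 or week-192 value as response when the scheduled values immediately before and after are both below 10^2 IU/ml on the allocated drug. Keep all other missing values, and Section F's toxicity discontinuations, as failures, and state that this is a composite endpoint.
2. Report loss by arm and reason. Pre-specify a tipping-point analysis of how many dropouts in each arm would have to be suppressed to remove significance, and attribute superiority to viral suppression only if it survives plausible values. Requiring only that a second analysis agree in direction would be too weak. In a simulation with equal 94% suppression and 50 per arm, using observed cases as the second analysis, false superiority fell only from about 17% to 15% (5/15% loss) and from about 36% to 27% (5/20% loss).
3. Reconcile the blinding statements in the opening of the Protocol section, Sections D and L, and Appendix A.

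The cost is a slightly more complex rule and one extra analysis. The HBV DNA values needed are already scheduled, so patients have no added visits or samples.

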The primary study endpoints will be a maintained full virological response after 48 weeks and 192 weeks of therapy (the two points of formal statistical analysis). The major secondary endpoint will be absence of a failure of therapy and absence of resistance mutations. Other endpoints to therapy will be loss of HBeAg, loss of HBsAg, normalization of serum ALT, improvements in histology activity index, improvements in hepatic fibrosis, improvement in Fibroscan scores and decrease in HVPg. Other endpoints will be improvement in symptom scores at 48 and 192 weeks.

Failure of therapy may be due to primary non-response, lack of virological response, breakthrough, or relapse, as defined below.

A **primary non-response** is defined as lack of decrease in HBV DNA levels by at least 1  $\log_{10}$  after at least 24 weeks of therapy in the absence of non-compliance.

A **failure in virological response** is defined as failure to suppress HBV DNA below  $10^4$  IU/ml after 48 weeks of therapy in the absence of non-compliance.

A **breakthrough** is defined as a  $\geq 1 \log_{10}$  IU/L increase in HBV DNA level from nadir in two consecutive samples at least one month apart in a patient with an initial full virological response in the absence of non-compliance.

A **relapse** is defined as a rise in HBV DNA levels to above  $10^4$  IU/ml or of ALT to above the normal range after therapy is stopped in a patient who previously had a maintained full virological response.

These definitions are all interlocking but help to define response and non-response rates and whether therapy has a sustained effect.

**Stopping therapy:** Therapy will be continued indefinitely or until one of the following endpoints are reached:

1. **Failure of therapy:** If HBV DNA levels remain consistently  $>10^4$  IU/ml after one year of continuous therapy, patients will be offered alternative therapy or the option to stop therapy. Alternative therapies may include switching to combination therapy if they were receiving monotherapy or switching to entecavir if receiving combination therapy. Patients who fail to respond may also elect to receive a course of peginterferon. These options are available at the NIH Clinical Center on an open-label basis.

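### Means are compared by an unadjusted t-test, with follow-up value or change left unstated; adjusting for baseline and stratum would generally sharpen the non-primary continuous comparisons

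*Combined protocol and SAP*

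**What the plan says.** Section I (Statistical analysis) deals with continuous measures in one sentence: "For comparison of means, Student's t-test will be used". No covariate or stratum enters, and the quantity tested is not stated. The baseline variables listed in the same section are candidate predictors of virological response, not adjustments to a comparison of means.

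Section F (Assessment of response) names among its other endpoints "improvements in histology activity index, improvements in hepatic fibrosis, improvement in Fibroscan scores and decrease in HVPg", and adds "Other endpoints will be improvement in symptom scores at 48 and 192 weeks". Section E (Monitoring) says "Bone mineral density will be re-assessed at 48 and 192 weeks"; bone density is a safety measure and is not on the Section F endpoint list.

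Section C (Initial evaluation) provides the matching baselines: HAI and Ishak fibrosis scores from the entry biopsy, Fibroscan, a bone density scan and, in patients with known or suspected portal hypertension, HVPG. Section D (Treatment) stratifies randomisation by HBeAg status and previous therapy, with a separate list for each of Groups A to E.

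**The concern.** A two-sample t-test does not use the strata, and it uses the baseline either not at all (on follow-up values) or with a fixed weight of one (on change). Either way, variation that the baseline could explain may remain in the error term. Strata may matter too. Section A1 requires naive patients to have an HAI of at least 4 and a fibrosis score of at least 1, while Sections A2 and A.3 set no such floor for previously treated patients. Pooled analyses therefore mix groups that may differ at entry.

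The numbers behind some of these comparisons are small. Sections D and E exclude salvage patients from the week-48 biopsy. That leaves Groups A and B, up to 20 patients each, or about 20 per arm. HVPG exists only in a subset of unstated size. At stake are confidence intervals wider than necessary, and a choice between two different t-tests left open until data are in hand.

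**Working it through.** **The plan's own figure.** Section I states: "We predict the rate of full virological response to combination therapy will be 94% and to tenofovir monotherapy to be 70% at 4 years". It continues: "A Fisher's exact test with a .05 two-sided significance level will have 86% power", "if the sample size in each group is 50". Full binomial enumeration of the two-sided Fisher test at 0.94 against 0.70 with 50 per arm gives 85.7%, so the stated 86% reproduces. It concerns the binary primary endpoint, and nothing below changes it. No power, SD, effect size or baseline correlation is given for any continuous measure.

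**Inputs for the continuous measures.** The baseline/follow-up correlation r is an assumption, taken from 0 to 0.7. Baseline and follow-up are assumed to have the same SD, σ. The number per arm is 40, because Section I names Groups A-D as the primary cohort and these hold up to 20 each (4 × 20 = 80).

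**Formulas.** Variance per patient, before dividing by sample size:

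- follow-up value: σ²
- change: 2σ²(1 − r)
- ANCOVA on baseline (large samples): σ²(1 − r²)

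The ratio of ANCOVA to the follow-up t-test is therefore 1 − r². The ratio of ANCOVA to the change t-test is (1 − r²) / [2(1 − r)] = (1 + r)/2.

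**Results.** Power comes from 4,000 simulated trials per row, with 40 per arm and arms balanced within four strata of 20 that have no effect on the outcome. The treatment effect is 0.634 SD, which gives the follow-up t-test 80% power. Monte Carlo error is about 0.6 points.

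| r (assumed) | ANCOVA / follow-up t, variance | ANCOVA / change t, variance | Power, follow-up t | Power, change t | Power, ANCOVA |
|---|---|---|---|---|---|
| 0 | 1.00 | 0.50 | 80.0% | 50.1% | 79.4% |
| 0.1 | 0.99 | 0.55 | 80.6% | 55.9% | 80.4% |
| 0.3 | 0.91 | 0.65 | 81.3% | 65.4% | 83.8% |
| 0.5 | 0.75 | 0.75 | 79.6% | 80.5% | 89.3% |
| 0.7 | 0.51 | 0.85 | 80.8% | 95.8% | 97.7% |

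Simulated type I error was 4.5% to 5.9% for ANCOVA and 4.6% to 5.8% for the two t-tests, so all three are valid. Because the strata had no effect here, the gain shown comes from the baseline alone.

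**Cost of adjusting.** At 40 per arm and r = 0, ANCOVA loses 80.0 − 79.4 = 0.6 points against the follow-up t-test. This relies on the arms being balanced within strata. A rougher closed-form approximation, which lets four covariates be imbalanced by chance, gives 77.8% against 80%, about 2 points. At 10 per arm (one group of 20, baseline as the only covariate, effect 1.325 SD) and r = 0, the figures are 80.3% and 77.6%, a loss of about 3 points. At r = 0.3 and the same size, ANCOVA is already level or slightly ahead (80.0% against 81.0%).

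**Which t-test is meant.** Under Hypotheses and Issues, the protocol describes the comparison of HBV DNA and ALT as one of the fall from baseline and its rate. Section F speaks of improvements and of a decrease. Both point to change, so the (1 + r)/2 column is the more relevant one.

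**The case against.** The case for leaving the sentence alone is a fair one.

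- **Scope.** The primary endpoint is binary. Section F also defines histological response as a binary outcome built on the change from the entry biopsy, and ALT normalisation and loss of HBeAg or HBsAg are binary. The documents do not say outright that HAI or fibrosis will be compared as means. This stands, and it confines the point to non-primary measures.
- **Baseline already enters.** If change is tested, the comparison is not wholly unadjusted. This stands, but a change score fixes the weight on baseline at one, which the table shows to be costly when r is low.
- **Correlations may be low.** Entry biopsies in salvage patients may be up to five years old (Sections A2 and A.3), and strong viral suppression may flatten late values. At r of 0 to 0.1 there is no gain over a follow-up t-test. This stands, and is why the range starts at 0.
- **Feasibility.** Full stratum terms may not be estimable in the HVPG subset, and a proportional-odds model for a seven-level fibrosis score may be sparse with about 40 week-48 biopsies. This stands and limits the fix.

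A reader might go further and infer that the t-test is biased, through regression to the mean or the different entry floors. The documents do not support that. Regression to the mean acts on both arms alike under randomisation, the entry floors differ between groups within which patients are randomised, and chance imbalance is variance that the t-test's interval already reflects. Week-48 histology involves naive patients only, so the mixing of naive and salvage patients does not arise there.

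**Conclusion.** The point holds as one of efficiency and completeness. Section I should say what is compared, and for the non-primary continuous measures baseline- and stratum-adjusted ANCOVA is generally the better analysis. With r assumed between 0 and 0.7, it reduces the variance to 0.50 to 0.85 of that of a change-score t-test and to 1.00 to 0.51 of that of a follow-up t-test. These figures assume equal SDs and rest on correlations that the documents do not supply.

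Two stronger readings are tempting and should not be drawn. One is that the plan wastes nearly half its patients: at r = 0.7 a follow-up t-test needs 1/0.51 = 1.96 times as many, or 96% more. But the protocol's wording favours change, for which the figure at the same r is 1/0.85 = 1.18, or 18% more. The other is that adjustment is free: it costs about 3 points of power at 10 per arm if baseline is uninformative. Neither the validity of the t-test nor the primary analysis is in question.

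**What to change.** Replace the t-test sentence in Section I with:

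> HAI, fibrosis score, Fibroscan, bone density and HVPG at weeks 48 and/or 192, as measured, will be compared between arms by ANCOVA with treatment, the baseline value and the randomisation stratification factors as covariates, reporting the adjusted mean difference and 95% CI; in small subsets such as HVPG, only the baseline value will be included.

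Keep HBV DNA out of this sentence. Section I predicts 70% to 94% of patients below 100 IU/ml at four years, and Section C gives an assay limit of 20 IU/ml, so late values will collect near the limit and suit neither a linear ANCOVA nor a t-test on means. It needs its own sentence giving the scale and the handling of values below the limit. Because the t-test sentence goes, the methods for ALT and symptom scores should also be stated. The rule that counts missing data as treatment failure does not tell the analyst what to do with a missing continuous value, and the new sentence does not settle that.

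The change needs no new visits, patients or measurements. Its statistical price is a few degrees of freedom: under 1 point of power at 40 per arm with arms balanced within strata, and about 3 points at 10 per arm, if the baseline is uninformative.
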